7.2.3 Unanticipated Problem (UP)

Per Stanford IRB, UPs are events involving risks to participants or others and must meet ALL 3 criteria below:

1. Unexpected: in terms of nature, severity, or frequency, given (a) the research procedures described in the protocol-related documents, and (b) the characteristics of the subject population being studied; AND
2. Related to participation in the research: or there is a reasonable possibility that the incident, experience, or outcome may have been caused by the procedures involved in the research; or if a device is involved, probably caused by, or associated with the device; AND
3. Harmful: suggests that the research places subjects or others at a greater risk of harm (including physical, psychological, economic, or social harm) than was previously known or recognized.

UPs generally will warrant consideration of substantive changes in the research protocol or informed consent process/document, or other corrective actions, in order to protect the safety, welfare, or rights of subjects or others.(27) Due to this, UPs will be reported promptly to Stanford IRB following the below guidelines.

A UP may also be an AE or SAE and can be noted as both on CRFs and in OnCore.

Reporting UPs

UPs should be entered into OnCore and reported within 24 hours of learning of the event.

7.2.4 AE Relationship to the Investigational Product:

Every effort will be made to determine the cause of each adverse event. The correlation between the investigational product and the adverse event will be classified as follows:

1. Probable

- a) The event follows a reasonable temporal sequence from administration of the investigational product;
- b) The event follows a known response pattern to the investigational product;
- c) The event cannot be reasonably explained by any of the following features:
 - the known characteristics of the subject's clinical state, or
 - other therapy administered
 - or the diagnostic/interventional procedure;
- d) There is evidence of partial or complete disappearance of the event after withdrawal of the product (positive challenge).
- e) The event follows a known response pattern to the investigational product but the event could have been produced by any of the following features:
 - the subject's clinical state, or
 - other therapy administered, or
 - the diagnostic/interventional procedure.
- f) The event does not meet any of the above criteria because of:
 - conflicting data and/or
 - dubious or insufficient/poor evidence, or
 - the event is not judged as related or not related.
- g) The event is either a pre-dose event or is definitely due to causes separate from the administration of the investigational product, i.e.
 - documented pre-existing condition
 - technical and manual procedural problems
 - concomitant medication
 - the subject's clinical state
 - the event is judged as not related and does not fall under any of the above points.

2. Possible

- 3. Not Related
- 4. Unknown

7.2.5 AE Action Taken:

- 0. None

1. Change in the investigational product administration (including brief interruption of administration of total dose and early termination of administration, i.e., dose reduction)
2. Drug treatment required (a medication was prescribed or changed; record in the Concomitant Medication section of the CRF)
3. Non-drug treatment required (a non-drug treatment was prescribed or changed, record under "Comments" in the Adverse Event section of the CRF)
4. Hospitalization or prolonged hospitalization
5. Diagnostic or clinical test(s) conducted (attach a copy of the results to the CRF)
6. Subject discontinued from the study

7.2.6 AE Subject Outcome:

1. Recovered without sequelae.
2. Recovered with sequelae (describe the sequelae under "Comments" in the Adverse Event section of the CRF)
3. Not Recovered, event on-going (follow the subject until a definite outcome can be determined. When follow-up data are collected, report follow-up information under "Comments" in the Adverse Event section of the CRF; if the event is serious, fill in a follow-up SAER)
4. Died (list primary cause of death under "Event Description" in the Adverse Event section of the CRF)

8 CORRELATIVE/SPECIAL STUDIES

8.1 Laboratory Correlative Studies

There are no Laboratory Correlative Studies

9 STUDY CALENDAR

	Enrollment	Baseline	0-7Days after the first fraction of radiotherapy treatment	2-4 Months from starting SABR
Informed consent	X ^a			
H&P	X ^{a,f}			
Eligibility	X ^a			
Documentation of Consent	X ^a			
ECOG PS	X ^{a,e}			
Study Registration	X ^a			
Simulation CT		X		
AE Evaluation		X ^{b,d}	X ^{b,d}	X ^{b,d}
Definity®/Ultrasound		X	X	X
B-HCG or urine pregnancy test	X ^{a,c}			

- a. Prior to study procedures.
- b. Baseline assessment prior to Definity© injection .
- c. Required for women who are not post-menopausal as defined in Appendix B and who are not excluded from possibility of pregnancy by a physician.
- d. Documented 30-60 minutes after Definity © injection
- e. ECOG specified in medical note prior to eligibility confirmation, defined in Appendix C.
- f. H&P done within 4 weeks of enrollment.

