3.5 Study Timeline

Definity®-enhanced ultrasound at baseline will be completed prior to delivery of SABR treatment. The patient will then be re-scanned 0-7 days post their first fraction of radiation treatment. An additional US scan will be performed 2-4 months (when patient comes to routine follow-up CT and PET-CT imaging).

Primary Completion:

The expected study completion timeline is within 24 months from when the study opens.

Study Completion:

The expected study completion timeline is within 24 months and 1 day from when the study opens.

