4 TREATMENT PLAN

Pregnancy Test

If the subject is female and of child-bearing potential, exclude the possibility of pregnancy by:

- testing serum β HCG or urine pregnancy test prior to the start of Definity® administration (the local laboratory may be used)
- obtaining surgical history (e.g., tubal ligation or hysterectomy)
- obtaining medical history (post-menopausal with a minimum of 1 year without menses).

See Appendix B.

Safety Assessments Adverse Events

We will record all untoward medical events in the Adverse Event section of the CRF. Only post-dose untoward medical occurrences will be tabulated as adverse events.

Imaging Procedures

The unenhanced ultrasound and Definity®-enhanced images will be performed, in the same session, using commercially available (FDA-approved) ultrasound systems with appropriate contrast-specific capabilities. The ultrasound examination, both unenhanced and contrast-enhanced should be performed by qualified personnel with at least 3 years of experience in liver ultrasound or Fellows with appointment in Stanford Radiology

Definity® will be administered intravenously into a central line or port or an upper extremity vein (e.g., a vein in the cubital fossa or dorsal aspect of the wrist or hand) using a catheter while observing aseptic technique. Immediately following the Definity® injection, 5 mL to 10 mL of saline will be administered to flush the intravenous line of any remaining contrast agent. Subjects will be monitored for any untoward medical occurrences listed in a study case report form or note for 30-60 min after Definity® injection is initiated.

Imaging parameters:

Contrast-specific imaging will be performed with an abdominal matrix-array transducer (PM mode, Philips iU22 with X6-1; Philips Ultrasound, Bothell Wash) which is a low-mechanical-index (MI) nonlinear imaging (MI, 0.06) that allows visualization of the micro-bubbles nondestructively. Time-gain controls will be aligned to the center line. Receive gain, dynamic range, image depth, and transmit focus will be optimized for each patient at the baseline examination, and then identical settings will be used at follow-up. Disruption-replenishment data will be collected for approximately 30 seconds following 1-second, 8-frame flash at an MI of 1.3.

Unenhanced Ultrasound

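### The calendar tests for pregnancy only at enrollment, so the 2-4 month Definity dose can be given on a result at least about two months old

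*Combined protocol and SAP*

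**What the plan says.** The calendar in Section 9 contains a row headed "B-HCG or urine pregnancy test". Its only mark is under Enrollment, with footnote a (done before study procedures) and footnote c, which begins "Required for women who are not post-menopausal as defined in Appendix B" and also exempts women in whom a physician has ruled out pregnancy. The Definity/ultrasound row is marked at three visits: baseline, 0-7 days after the first fraction, and "2-4 Months from starting SABR".

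Section 3.5 fixes the order at the start: "Definity®-enhanced ultrasound at baseline will be completed prior to delivery of SABR treatment".

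Section 4, under Pregnancy Test, lists three ways to exclude pregnancy in a woman of child-bearing potential: surgical history, medical history, or a serum or "urine pregnancy test prior to the start of Definity® administration". It does not say whether this means the first dose or every dose.

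Section 3.2.6 excludes women who are pregnant or seeking pregnancy. Section 4.2 withdraws a subject who comes to meet an exclusion criterion during the study. Neither schedules a check after enrollment.

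**The concern.** The protocol treats pregnancy as a reason not to give the agent and puts a test in place before study procedures begin. The first two doses lie close to the start of SABR; the third comes months later. A site that follows the calendar exactly gives that third dose with no fresh check. A known or reported pregnancy is handled by 4.2, but one that is new and unrecognised would pass through, because no scheduled procedure looks for it. At stake is participant protection at one study-added dose. No endpoint or estimate is affected.

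**Working it through.** The plan gives no figure for the age of the test result, so there is none to reproduce. The check is calendar arithmetic.

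**Inputs**
- Day 0 is the first SABR fraction, taken as the start of SABR.
- The test precedes study procedures (Section 9, footnote a), and the baseline scan precedes SABR (3.5). The test therefore falls L days before day 0, with L at least 0. The documents do not give L.
- Dose 2 is on day 0 to 7; dose 3 is 2 to 4 months after day 0 (Section 9).
- Planned sample size: 20 (12.4).

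**Formula**

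Age of result at a dose = L + (day of that dose).

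**Lower bound at dose 3 (L = 0)**
- One month = 365.25 / 12 = 30.44 days.
- 2 months: 60.9 days on average; 59 to 62 days depending on the calendar months involved.
- 4 months: 121.8 days on average; 120 to 123 by calendar months.

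The strict minimum is thus 59 days, and about 61 is the average-month figure. Any positive L adds to it.

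**Range for assumed values of L** (illustrations, not protocol figures)

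| Test to SABR, L (days) | Age at dose 2 (days) | Age at dose 3 (days) |
|---|---|---|
| 0 | 0-7 | 60.9-121.8 |
| 7 | 7-14 | 67.9-128.8 |
| 14 | 14-21 | 74.9-135.8 |
| 28 | 28-35 | 88.9-149.8 |

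The dose 2 column shows that being within 7 days of the first fraction does not by itself make the result recent at that visit, because the test is tied to enrollment and not to the first fraction.

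**Spacing of doses 2 and 3**

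Smallest gap: 61 - 7 = 54 days, or 59 - 7 = 52 days with the shortest calendar months.

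**Number affected**

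One later dose per woman meeting footnote c. How many such women will enroll is not given; the count lies between 0 and 20.

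**The case against.** The strongest reply is that the documents are consistent and breach no standard of their own. The calendar shows one test before dosing, and Section 4 asks for exclusion of pregnancy before Definity starts. No section sets a maximum age for the result, the contraindications in 5.1 do not list pregnancy, and no fetal-risk figure is given. Women seeking pregnancy are already excluded, and a known pregnancy leads to withdrawal. On this view a repeat test is a preference.

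Much of that stands. A reader might infer that Section 4 demands a test at each session and so contradicts the calendar. The argument would be that the protocol uses the singular for steps repeated at every visit: "Baseline assessment prior to Definity© injection" and "Documented 30-60 minutes after Definity © injection" in the calendar footnotes, and "Immediately following the Definity® injection, 5 mL to 10 mL of saline will be administered" in Section 4. Section 7.2.1 even describes the post-dose observation as following each injection. This makes a per-session reading possible but not equally likely. Those two footnotes apply at three visits because the calendar places them in three columns, whereas the pregnancy test sits in one. The natural reading is a single check before the first dose.

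A reader might also infer that the result has expired by dose 3. That needs a validity window, and the documents contain none.

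What the reply does not remove is the gap itself. Excluding women who seek pregnancy does not cover an unplanned one, and 4.2 works only once the pregnancy is known. The third scan coincides with routine CT and PET-CT (3.5), but the protocol does not say that pregnancy screening takes place there or link any to the Definity dose.

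**Conclusion.** The point holds as a minor gap in participant protection. Followed exactly, the calendar allows a woman meeting footnote c to receive the third dose on a result at least 59 to 62 days old, plus the unstated interval from enrollment to SABR, with nothing scheduled to detect a new, unrecognised pregnancy. Section 4 agrees with the calendar on its natural reading but leaves the matter unsaid and requires no repeat.

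The conclusion rests on the calendar marks, the ordering in 3.5, and taking the first fraction as the start of SABR. It does not assert a direct contradiction between sections, a result older than the protocol permits, or any known level of fetal harm; the documents support none of these. Nor does it declare dose 2 safe, since the age of the result at that visit has no stated upper limit. The number of women affected may be zero.

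**What to change.** 1. In Section 9, add a mark in the pregnancy-test row at the 2-4 month visit for women meeting footnote c, as a urine test before the injection.
2. In Section 4, state that pregnancy is to be excluded before the first Definity dose and again before the 2-4 month dose.
3. In the same place, give a maximum age in days, chosen by the sponsor, for the result relied on at the baseline and 0-7 day doses. Calling it a recent result would only replace one ambiguity with another.

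The cost is one calendar mark, a reworded Section 4, and about one extra urine test per woman meeting footnote c who reaches the 2-4 month visit: 1 x 0 = 0 to 1 x 20 = 20 tests at most in the trial. Slightly more would be needed if an enrollment result falls outside the stated window at an early dose. No invasive procedure is added.

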10 MEASUREMENTS

For clinicaltrials.gov and Stanford Clinical Trials Directory compliance

10.1 Primary and Secondary Outcome measures

10.1.1 Relevant Subset

All patients will be considered for the secondary outcome.

10.1.2 Measurement Definition

Primary Objective:

The primary objectives of this pilot study is to (1) determine the feasibility and reproducibility of 3D contrast enhanced ultrasound imaging in liver patients undergoing Stereotactic Ablative Radiotherapy and (2) evaluate whether there are treatment induced early changes in imaging metrics derived from 3D contrast enhanced ultrasound.

10.1.3 Measurement Methods

Contrast Agent Administration

The US contrast agent will be perflutren lipid microspheres (Definity; Lantheus Medical Imaging, North Billerica, Mass). Patients will receive an infusion of 1.3 mL of perflutren lipid microspheres diluted in 50 mL of saline delivered up to 10 mL/min by using an injection pump (Medfusion 3500; Smiths Medical, Dublin Ohio). Two minutes will be allowed for the infusion to reach a steady level before disruption-replenishment measurements were performed.

Imaging System Parameters

Contrast-specific imaging will be performed with an abdominal matrix-array transducer (PMPI mode, Philips iU22 with X6-1; Philips Ultrasound, Bothell Wash). Low-mechanical-index (MI) nonlinear imaging (MI, 0.06) will allow visualization of the microbubbles nondestructively. Persistence and other post-processing will be disabled to minimize temporal and spatial averaging. Time-gain controls will be aligned to the center line. Receive gain, dynamic range, image depth, and transmit focus will be optimized for each patient at the baseline examination, and then identical settings will be used at follow-up. Disruption-replenishment data will be collected for approximately 30 seconds following each 1-second, 8-frame flash at an MI of 1.3. Frame rates ranged from 7 to 12 Hz. Data will be stored in a compressed “native” format to allow linearization.

10.1.4 Measurement Time Points

The probe will be held steady throughout each acquisition. During the infusion, continuous 3D data will be collected and two disruption-replenishment acquisitions will be performed.

10.1.5 Image analysis and derived measures

Volume of interest (VOIs) encompassing the lesions will be defined on the 3D DCE-US. After linearization of the 3D DCE-US signal (to make it proportional to contrast concentration), time intensity curves (TIC) will be generated for the mean contrast concentration within the VOI. After standard TIC fit curve parameters will be extracted to serve as measures that describe perfusion. These measures include: relative blood volume, mean flow velocity, and relative blood flow = relative blood volume x mean flow velocity.

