1 OBJECTIVES

1.1 Primary Objective

The primary objectives of this prospective pilot study is to (1) determine the feasibility and reproducibility of 3D contrast enhanced ultrasound imaging in liver cancer patients undergoing Stereotactic Ablative Radiotherapy and (2) evaluate whether there are treatment induced early changes in imaging metrics derived from 3D contrast enhanced ultrasound. This study will provide valuable insight as to the potential of baseline and/or early post-treatment 3D ultrasound perfusion characteristics (measurements of blood-flow) of primary and metastatic liver tumors to predict tumor response to Stereotactic Ablative Radiotherapy. Our underlying goal is to assess whether early perfusion changes at 0-7 days after SABR initiation can be used as a non-invasive early biomarker for treatment response assessment.

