2.4 Study Design

For clinicaltrials.gov and Stanford Clinical Trials Directory compliance

This is a pilot, single-center study in subjects with liver tumors. The primary objectives of this prospective pilot study is to (1) determine the feasibility and reproducibility of 3D contrast

enhanced ultrasound imaging in liver cancer patients undergoing Stereotactic Ablative Radiotherapy and (2) evaluate whether there are treatment induced early changes in imaging metrics derived from 3D contrast enhanced ultrasound. This study will provide valuable insight as to the potential of baseline and/or early post-treatment 3D ultrasound perfusion characteristics (measurements of blood-flow) of primary and metastatic liver tumors to predict tumor response to Stereotactic Ablative Radiotherapy.

The target lesion will be located at the simulation CT scan for treatment planning. Prior to Definity® administration, gray scale and Doppler (color or power imaging) ultrasound investigations of the target lesion will be performed using commercially available ultrasound equipment and standard techniques (B-mode or Harmonic imaging) to study the anatomy of the target lesion and surrounding parenchyma.

Immediately after the unenhanced ultrasound evaluation, contrast-enhanced ultrasound will be performed, according to the procedures described to study the lesion vascularity in comparison to the surrounding parenchyma. Definity® will be administered intravenously through a central line or in a peripheral vein.

Unenhanced ultrasound and Definity®-enhanced ultrasound images will be recorded and stored anonymously.

The primary analysis will be based on comparison of the readout (perfusion parameters of the lesion) at baseline, at 0-7 days after the first fraction of radiotherapy treatment, 2-4 months following the start of radiotherapy, and the clinical outcome of the patient, including findings on routine CT and PET-CT imaging.

This is a Single Group, Open Label Study designed to evaluate to evaluate as a primary outcome feasibility and efficacy.

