- Histogram analysis and summary statistics (mean, median, variance, and maximum) of the relative changes (difference/average) of repeated 3D DCE-US measures. (Small variance and zero mean of the relative changes will be indicative of highly reproducible 3D DCE-US measures).
- Histogram analysis and summary statistics (mean, median, variance, and maximum) of the relative changes (difference/baseline) in 3D DCE-US measures before and after SABR. Large mean differences will be indicative of treatment (SABR) effect.

- Calculation of proportion of 3D DCE-US examinations in which fusion to CT is possible with tracking of the ultrasound transducer. Calculation of proportion of 3D DCE-US examination in which repeated scans is successful. These proportions are metrics of feasibility (target 80%-90%). Successful fusion to CT in particular is important metric is 3D DCE-US is to be explored as add-on imaging for treatment planning in further studies.

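### With lesion-only measures in a single group and one pre-SABR session, a between-visit shift shared by lesion and liver cannot be told from a lesion-specific change, yet section 12.3 reads a large mean change as a SABR effect

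*Combined protocol and SAP*

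**What the plan says.** All references are to the combined protocol and SAP.

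- **Aim.** Section 1.1, objective (2), is to "evaluate whether there are treatment induced early changes in imaging metrics derived from 3D contrast enhanced ultrasound".
- **Design.** Section 2.4: "This is a Single Group, Open Label Study". The schema gives three scan sessions: one before radiotherapy, one 0-7 days after the first fraction, and one 2-4 months after the start.
- **Purpose of the contrast scan.** Section 2.4 says it is done "to study the lesion vascularity in comparison to the surrounding parenchyma".
- **Readout.** The same section continues: "The primary analysis will be based on comparison of the readout (perfusion parameters of the lesion) at baseline".
- **Region measured.** Section 10.1.5: "Volume of interest (VOIs) encompassing the lesions will be defined on the 3D DCE-US", after which "time intensity curves (TIC) will be generated for the mean contrast concentration within the VOI". The outputs are listed: "These measures include: relative blood volume, mean flow velocity, and relative blood flow = relative blood volume x mean flow velocity". No liver VOI, lesion-to-liver ratio or other normalisation appears in sections 10 or 12.
- **Change analysis.** Section 12.3 summarises the before/after change divided by baseline, by histogram, mean, median, variance and maximum, and adds: "Large mean differences will be indicative of treatment (SABR) effect".
- **Between-visit control.** Sections 4 and 10.1.3 keep gain, dynamic range, depth and focus at their baseline settings. Section 10.1.4 places both repeat acquisitions within one infusion.

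**The concern.** An uncontrolled before/after comparison credits to treatment whatever else differs between the visits. Here the visits are days to months apart. A patient's circulation can differ between them, and so can the contrast level reaching the liver: section 10.1.3 gives the infusion rate only as a ceiling of 10 mL/min, and section 4 gives no rate. Because the signal is linearised to be proportional to contrast concentration, a different contrast level at follow-up would scale blood volume and blood flow in lesion and liver alike. It need not alter mean flow velocity.

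The surrounding liver in the same 3D acquisition could show whether such a shift took place. Section 2.4 says that tissue is looked at, but no measure of it reaches an endpoint. At stake are the answer to objective (2) and the variance of change that section 12.3 intends to pass on to the sample size of later studies.

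**Working it through.** **Plan's own figure.** There is none to reproduce. Section 12.4 gives 20 patients, and section 12.5 says there was too little information for a calculation. No SD, effect size, alpha or power is stated. Everything below except n = 20 and the two repeats per session is an assumption, shown over a range.

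**Step 1. What the existing controls cover.** Fixed scanner settings remove part of the technical variation, but not physiology or contrast delivery. Repeats within one infusion show same-session noise only. With one pre-SABR session there is no untreated interval in which to see between-visit variation.

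**Step 2. Size if the visit factor is fully shared.** Let each visit multiply lesion and liver by the same log-normal factor with log-SD s, independent between visits, with no SABR effect and no other noise. Follow-up/baseline is then log-normal with log-variance 2s², so for (follow-up − baseline)/baseline:

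- SD = exp(s²) × √(exp(2s²) − 1)
- standard error of the mean = SD/√20
- mean = exp(s²) − 1

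| s | per-patient SD | standard error, n = 20 | mean with no effect |
|---|---|---|---|
| 0.15 | 1.023 × 0.215 = 0.22 | 0.049 | 0.02 |
| 0.20 | 1.041 × 0.289 = 0.30 | 0.067 | 0.04 |
| 0.30 | 1.094 × 0.444 = 0.49 | 0.109 | 0.09 |

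The main result is spread. The non-zero mean comes from dividing by a noisy baseline. A shift in the same direction in all patients would enter the mean in full and would not average out at any n.

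**Step 3. What same-session repeats miss.** On the log scale, let w be the same-session SD and d the between-day SD. The repeat difference has SD √2·w. The visit-to-visit change, averaging two repeats per visit, has SD √(2d² + w²) with no SABR effect. With w = 0.05 the repeat SD is 0.071, while the change SD is 0.150, 0.287 and 0.427 for d = 0.1, 0.2 and 0.3. That is 2.1, 4.1 and 6.0 times larger.

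**Step 4. When a liver reference reduces spread.** Let rho be the correlation of the lesion and liver day effects, with equal SDs in both tissues and independent same-session noise. The change in the log lesion/liver ratio has SD √(4d²(1 − rho) + 2w²). With w = 0.05:

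| d | lesion only | ratio, rho 0 | rho 0.5 | rho 0.8 | rho 0.95 |
|---|---|---|---|---|---|
| 0.1 | 0.150 | 0.212 | 0.158 | 0.114 | 0.084 |
| 0.2 | 0.287 | 0.406 | 0.292 | 0.192 | 0.114 |
| 0.3 | 0.427 | 0.604 | 0.430 | 0.277 | 0.152 |

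Setting the two variances equal gives the break-even rho = 0.5 + w²/(4d²). For w = 0.05 and d = 0.2 this is 0.5 + 0.0025/0.16 = 0.52. For w = d = 0.10 it is 0.5 + 0.01/0.04 = 0.75.

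**The case against.** The strongest reply has four parts.

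1. **The sections agree.** A reader might infer that 2.4 contradicts 10.1.5. It does not. The parenchyma comparison is given as a purpose of the scan, and the same section names lesion parameters as the primary readout. This stands: the comparison is announced and left unused.

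2. **The benefit of a ratio is not shown.** A reader might infer that a lesion/liver ratio removes the problem. Full cancellation follows only if the day effect is wholly shared. Step 4 shows no gain at rho = 0.5 and more noise below it, and the documents give none of w, d or rho. This stands too, and is why the ratio should be reported and not relied on.

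3. **The ratio could mislead.** Making a change in the ratio a condition for reading a SABR effect is tempting, but nearby liver may receive dose. If it moved with the lesion, the ratio would hide a real effect. Requiring the VOI to lie outside the high-dose region would also depend on ultrasound-to-CT fusion, which is itself the secondary feasibility outcome, with a target of 80%-90% in section 12.3. Both points stand.

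4. **The study is exploratory.** There is no formal test, the attribution wording in 12.3 is hedged, and the variance of change is already reported. This limits the consequence without removing it. The reported variance cannot separate visit-to-visit noise from differing responses, and the attribution sentence has no reference to rest on.

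In the other direction, a reader might take relative blood volume to mean relative to liver. Section 10.1.5 states no such reference and takes the measure from the lesion curve.

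**Conclusion.** The point holds as a limit on attribution. Under sections 10.1.5 and 12.3, a shift common to lesion and liver and a lesion-specific change give the same number and the same reading, and nothing else in the plan separates them.

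The size is unknown. The range of 22% to 49% per patient, or 5 to 11 points on the mean of 20, rests on an assumed fully shared factor with log-SD 0.15 to 0.30. It describes mainly added spread, plus the upward pull of 2% to 9% from dividing by a noisy baseline. The documents do not support the stronger inference that ordinary day-to-day variation would produce a large false mean effect. That would need a shift systematic across patients. Contrast delivery is one possible route, but the documents give no evidence that such a shift occurs. The change is worth making because it serves objective (2) with data already stored; its absence does not invalidate the pilot.

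**What to change.** - **Section 10.1.5.** Add a reference VOI in non-tumour liver in the same stored acquisition, where the field of view allows, as far from the target as possible and with its location recorded. Derive the same three measures from it.
- **Sections 12.2 and 12.3.** Report the before/after change for lesion, reference liver and lesion/liver ratio side by side. Keep the lesion measure as the primary readout, and do not make the ratio a condition for interpreting it.
- **Section 12.3, attribution sentence.** Say that a large lesion change is consistent with a SABR effect and is interpreted together with the change in reference liver.

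**Cost.** One extra VOI per acquisition: at most 20 patients × 3 visits × 2 acquisitions = 120, if one target is imaged per visit. No further scan, contrast or staff is needed. 

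**Downsides.** The ratio carries the noise of the reference and reduces spread only when the lesion-liver between-visit correlation is above about 0.5, or higher if same-session noise is large. Nearby liver may receive dose, and some acquisitions may contain no suitable region, so the number with a usable reference should be reported. A second pre-SABR session would measure between-day variation directly, but needs another scan and is not required for this change.
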